5.2 Exclusion Criteria

A subject who meets any of the following criteria is ineligible for the study:

1. The subject has received cytotoxic chemotherapy or biologic agents (e.g., cytokines or antibodies) within 14 days, or nitrosoureas/mitomycin C within 6 weeks before the first dose of study treatment;
2. Prior treatment with cabozantinib or erlotinib;
3. Radiation therapy for bone metastasis within 2 weeks, any other external radiation therapy within 4 weeks before the first dose of study treatment. Systemic treatment with radionuclides within 6 weeks before the first dose of study treatment. Subjects with clinically relevant ongoing complications from prior radiation therapy are not eligible;
4. Receipt of any type of small molecule kinase inhibitor (including investigational kinase inhibitor) within 14 days before the first dose of study treatment;
5. The subject has received any other type of investigational agent within 28 days before the first dose of study treatment;
6. Known brain metastases or cranial epidural disease unless adequately treated with radiotherapy and/or surgery (including radiosurgery) and stable for at least 4 weeks before the first dose of study treatment. Eligible subjects must be neurologically asymptomatic and without corticosteroid treatment at the time of the start of study treatment;
7. Concomitant anticoagulation at therapeutic doses with oral anticoagulants (e.g., warfarin, direct thrombin and Factor Xa inhibitors) or platelet inhibitors (e.g., clopidogrel);

Note: Low-dose aspirin for cardioprotection (per local applicable guidelines) and low-dose LMWH are permitted. Anticoagulation with therapeutic doses of LMWH is allowed in subjects who are on a stable dose of LMWH for at least 6 weeks before first dose of study treatment, and who have had no clinically significant hemorrhagic complications from the anticoagulation regimen or the tumor.

8. The subject has experienced any of the following:

CONFIDENTIAL

- a. clinically-significant GI bleeding within 6 months before the first dose of study treatment;
 - b. hemoptysis of ≥ 0.5 teaspoon (2.5ml) of red blood within 3 months before the first dose of study treatment;
 - c. any other signs indicative of pulmonary hemorrhage within 3 months before the first dose of study treatment; and
 - d. clinically confirmed history of interstitial lung disease (ILD).
9. The subject has radiographic evidence of cavitating pulmonary lesion(s);
10. The subject has tumor invading a major blood vessel (encasement of local vascular structures is not exclusionary).
11. The subject has evidence of tumor invading the GI tract (esophagus, stomach, small or large bowel, rectum or anus), or any evidence of endotracheal or endobronchial tumor within 28 days before the first dose of cabozantinib which in the opinion of the investigator places the subject at greater risk of perforation.
12. The subject has uncontrolled, significant intercurrent or recent illness including, but not limited to, the following conditions:
- a. Cardiovascular disorders including:
 - i. Congestive heart failure (CHF): New York Heart Association (NYHA) Class III (moderate) or Class IV (severe) at the time of screening;
 - ii. Concurrent uncontrolled hypertension defined as sustained blood pressure (BP) > 150 mm Hg systolic or > 100 mm Hg diastolic despite optimal antihypertensive treatment within 7 days of the first dose of study treatment;
 - iii. Any history of congenital long QT syndrome;
 - iv. Any of the following within 6 months before the first dose of study treatment:

CONFIDENTIAL

- unstable angina pectoris;
 - clinically-significant cardiac arrhythmias;
 - stroke (including transient ischemic attack (TIA), or other ischemic event);
 - myocardial infarction.
- b. GI disorders particularly those associated with a high risk of perforation or fistula formation including:
- i. Tumors invading the GI tract, active peptic ulcer disease, inflammatory bowel disease (e.g., Crohn's disease), diverticulitis, cholecystitis, symptomatic cholangitis or appendicitis, acute pancreatitis or acute obstruction of the pancreatic duct or common bile duct, or gastric outlet obstruction
 - ii. Abdominal fistula, GI perforation, bowel obstruction, intra-abdominal abscess within 6 months before first dose of study treatment
- Note: Complete healing of an intra-abdominal abscess must be confirmed prior first dose of study treatment
- c. Other clinically significant disorders that would preclude safe study participation;
13. Major surgery within 12 weeks before the first dose of study treatment. Complete wound healing from major surgery must have occurred 1 month before the first dose of study treatment. Minor surgery (including uncomplicated tooth extractions) within 28 days before the first dose of study treatment with complete wound healing at least 10 days before the first dose of study treatment. Subjects with clinically relevant ongoing complications from prior surgery are not eligible;
14. QTcF > 500 msec within 1 month before the first dose of study treatment:
- a. Three ECGs must be performed for eligibility determination. If the average of these three consecutive results for QTcF is ≤ 500 msec, the subject meets eligibility in this regard.
15. Pregnant or lactating females;

CONFIDENTIAL

16. Active smoker;
17. Inability to swallow intact tablets;
18. Previously identified allergy or hypersensitivity to components of the study treatment formulations;
19. Diagnosis of another malignancy within 2 years before the first dose of study treatment, except for superficial skin cancers, or localized, low grade tumors deemed cured and not treated with systemic therapy; malignancy felt by investigator to potentially affect subject survival or ability to evaluate disease response.

6 STUDY ASSESSMENTS AND PROCEDURES

The following schedule of assessments applies to all subjects (see Section 6.1). More frequent assessments should be obtained if clinically indicated.

CONFIDENTIAL

6.1 Schedule of Assessments

| | Pre-Treatment Period | | Study Treatment Period (cycles done every 28 ± 5 days) | | | | | Post-Treatment Period | Survival Follow-Up |
|---|---|--|--|------------|------|-------|---|------------------------------|--|
| | Within 28 days before 1 st Dose of Study Treatment | Within 7 days before 1 st dose of Study Treatment | Cycle 1/Day 1 | Cycle 1D15 | C2D1 | C2D15 | C3D1 and beyond will be done every 4 weeks (± 5 days) | 30 - 37 Days after last dose | Every 3 months for up to 2 years after treatment discontinuation |
| Administrative Procedures | | | | | | | | | |
| Informed consent | X | | | | | | | | |
| Inclusion/exclusion criteria | X | | | | | | | | |
| Demographics | X | | | | | | | | |
| Medical and cancer history | X | | | | | | | | |
| Registration | X | | | | | | | | |
| Prior and concomitant medication review | X | X | X | X | X | X | X | X | |
| Safety follow-up | | | | | | | | X | |
| Survival follow-up | | | | | | | | | X ¹ |
| Clinical Procedures/Assessments | | | | | | | | | |
| Adverse events/patient drug compliance | X ² | | X | X | X | X | X | X ³ | |
| Physical examination ⁴ | X | | X | X | X | X | X | X | |
| Vital signs ⁵ | | X | X | X | X | X | X | X | |
| ECOG performance status | X | | X | X | X | X | X | X | |
| 12-lead ECG | X | X | | | X | | X | | |

CONFIDENTIAL

| | Pre-Treatment Period | | Study Treatment Period (cycles done every 28 ± 5 days) | | | | | Post-Treatment Period | Survival Follow-Up |
|---|---|--|--|------------|------|-------|---|------------------------------|--|
| | Within 28 days before 1 st Dose of Study Treatment | Within 7 days before 1st dose of Study Treatment | Cycle 1/Day 1 | Cycle 1D15 | C2D1 | C2D15 | C3D1 and beyond will be done every 4 weeks (± 5 days) | 30 - 37 Days after last dose | Every 3 months for up to 2 years after treatment discontinuation |
| Laboratory Assessments | | | | | | | | | |
| Complete blood count with differential | | X | | X | X | X | X | X | |
| Comprehensive serum chemistry panel | | X | | X | X | X | X | X | |
| Urinalysis with UCP | | X | | X | X | X | X | X | |
| PT/INR, PTT | | X | | X | X | X | X | | |
| TSH, free T3, free T4 | | X | | X | X | X | X | | |
| CA19-9 | | X ¹¹ | | | X | | X | | |
| Pregnancy test (urine or serum) ⁹ | | X | | | X | | X | X | |
| Treatment | | | | | | | | | |
| Cabozantinib and erlotinib administration | | | | X (daily) | | | | | |
| Disease Assessment | | | | | | | | | |
| Contrast enhanced CT or MRI ⁶ | X | | | | | | X (every 8 weeks) | | |
| Archival Tissue Collection/Correlative Studies | | | | | | | | | |
| Blood sample collection ⁸ | | | X ¹⁰ | X | X | | X | | |
| Tissue sample collection ⁸ | X ⁷ | | | | | | | | |

CONFIDENTIAL

Footnotes:

1. Follow-up may be done by medical record review or phone call to subject and/or next of kin.
2. Subjects will be monitored for adverse events (AEs) from the time of first study intervention (i.e., biopsy, if needed, or treatment, whichever comes first).
3. Additional follow-up will occur for subjects with AEs related to study treatment that are ongoing at the time of this visit, and for subjects with SAEs related to study treatment that occur after the time of this visit.
4. A Full physical exam will be done in the pre-treatment period and on Cycle 1/Day 1. Physical exams may also be done by the investigator or qualified designee throughout participation in the trial as clinically indicated.
5. Vital signs include: height (at screening only), weight, temperature, pulse, respiratory rate, and blood pressure.
6. All sites of known disease must be assessed.
7. Patients will be asked for archival tissue during the screening period. Archival tissue is required pre-treatment as part of study eligibility to test for EGFR and c-MET expression. KRAS will also be tested if previous KRAS testing was not done or results are unknown AND there is adequate tissue available from tissue collected at screening
8. Only samples collected from eligible patients during the screening period will be utilized for the correlative studies which are outlined in this trial. Samples collected from ineligible patients during screening will be discarded.
9. Only for women of childbearing potential.
10. This sample may be collected any time after enrollment so long as it occurs before the patient takes his/her first dose of study medication on Cycle 1/Day 1.
11. The window for this test is within 28 days of starting treatment.

CONFIDENTIAL

6.2 Pre-Treatment Period

During the Pre-Treatment Period, subjects are consented and qualified (screened) for the study. Informed consent must be obtained before initiation of any clinical screening procedure that is performed solely for the purpose of determining eligibility for this study. There is a separate screening consent for this trial. Evaluations performed as part of routine care before informed consent can be considered as screening evaluations if done within the defined screening period.

Study eligibility is based on meeting all of the study inclusion criteria and none of the exclusion criteria at screening and on Study Day 1 before study treatment administration. For each subject, the Pre-Treatment Period ends upon receipt of the first dose of study treatment or final determination that the subject is ineligible for the study.

The following assessments will be conducted before subjects receive their first dose of cabozantinib and erlotinib on this protocol:

6.2.1 Administrative Procedures

6.2.1.1 Recruitment and Registration

Applicable regulatory documents must be completed and on file prior to registration of any subjects. Potential patients will be identified in the Oncology outpatient clinics or by referrals from outside physicians. Patients who appear to be eligible for this trial will undergo the Informed Consent Process and be screened for eligibility utilizing the Eligibility Criteria.

6.2.1.2 Informed Consent

The Investigator must obtain documented consent from each potential subject prior to participating in a clinical trial.

Consent must be documented by the subject's dated signature or by the subject's legally acceptable representative's dated signature on a consent form along with the dated signature of the person conducting the consent discussion.

A copy of the signed and dated consent form should be given to the subject before participation in the trial.

The initial informed consent form, any subsequent revised written informed consent form and any written information provided to the subject must receive the IRB's approval in advance of use. The subject or his/her legally acceptable representative should be informed in a timely manner if new information becomes available that may be relevant to the subject's willingness to

CONFIDENTIAL

continue participation in the trial. The communication of this information will be provided and documented via a revised consent form or addendum to the original consent form that captures the subject's dated signature or by the subject's legally acceptable representative's dated signature if the new information would affect the subject's willingness to continue participation in the study as determined by the IRB.

Specifics about a trial and the trial population will be added to the consent form template at the protocol level.

The informed consent will adhere to IRB requirements, applicable laws and regulations and Sponsor requirements.

6.2.1.3 Inclusion/Exclusion Criteria

The completed Eligibility Checklist will be forwarded to the Indiana University Simon Cancer Center (IUSCC) Clinical Trials Office (CTO) designee for eligibility verification.

6.2.1.4 Medical and Cancer History

A medical history will be obtained by the investigator or qualified designee during the screening period. Medical history will include all active conditions, and any condition diagnosed within the prior 10 years that are considered to be clinically significant by the Investigator. Details regarding the disease for which the subject has enrolled in this study will be recorded separately and not listed as medical history.

The investigator or qualified designee will obtain prior and current details regarding cancer disease status and will review all prior cancer treatments including systemic treatments, radiation, and surgeries.

6.2.1.5 Registration

The original signed IRB approved Informed Consent Document and completed Eligibility Checklist will be forwarded to the IUSCC CTO designee for eligibility verification and registration in the OnCore[®] database. Notification will be sent to the Principal Investigator (PI), treating physician and research nurse when registration is complete to confirm registration and inform them of the subject ID number.

6.2.1.6 Prior and Concomitant Medications Review

During the screening period, the investigator or qualified designee will review prior medication use (including prescription and over-the-counter medications, transfusions, vitamins, herbal

CONFIDENTIAL

remedies, and nutritional supplements and any protocol-specified washout requirement) and record prior medication taken by the subject within 28 days before written informed consent. Treatment for the disease for which the subject has enrolled in this study will be recorded separately and not listed as a prior medication.

The investigator or qualified designee will record medication, if any, taken by the subject during the trial. All medications related to reportable SAEs should be recorded as defined in Section 7.1.4.

6.3 Treatment Period

During the Treatment Period subjects will receive cabozantinib and erlotinib until either disease progression, the occurrence of unacceptable drug-related toxicity or for other reason(s) for subject withdrawal as described in Section 3.6.

If the subject is unable to have a study assessment taken within the defined time window due to an event outside of his or her control (e.g., clinic closure, personal emergency, inclement weather, vacation), the assessment should be performed as close as possible to the required schedule.

Regular tumor assessments should be performed in accordance to the guidelines in Section 6.3.1.8 to determine if PD is present.

The Treatment Period ends when a subject receives his or her last dose of study treatment; the subject then enters the Post-Treatment Period.

6.3.1 Clinical Procedures

6.3.1.1 Adverse Event Monitoring

Subjects should be instructed to immediately inform the PI of any AEs. Subjects experiencing dizziness, sleepiness, or other symptoms that could influence alertness or coordination should be advised not to drive or operate other heavy machinery.

The investigator or qualified designee will assess each subject to evaluate for potential new or worsening AEs as specified in the Schedule of Assessments and more frequently if clinically indicated. Adverse events will be graded and recorded throughout the study and during the follow-up period according to NCI CTCAE Version 4.03. Toxicities will be characterized in terms regarding seriousness, causality, toxicity grading, and action taken with regard to trial treatment.

CONFIDENTIAL

Please refer to Section 7.1 for detailed information regarding the assessment and recording of AEs.

6.3.1.2 Physical Exam

The investigator or qualified designee will perform a complete physical exam during the screening period and on Cycle 1/Day 1. Clinically significant abnormal findings should be recorded as medical history. Physical exams may also be done by the investigator or qualified designee throughout participation in the trial as clinically indicated.

6.3.1.3 Vital Signs

The investigator or qualified designee will take vital signs at screening and per the Schedule of Study Assessments in Section 6.1. Vital signs should include: height at screening only, weight, temperature, pulse, respiratory rate, and blood pressure.

6.3.1.4 Eastern Cooperative Oncology Group (ECOG) Performance Scale

The investigator or qualified designee will assess ECOG status at screening and per the Schedule of Study Assessments in Section 6.1.

6.3.1.5 Electrocardiogram (ECG)

The investigator or qualified designee will perform a 12-lead ECG at screening and every 4 weeks beginning Cycle 2/Day 1. Up to 2 ECGs may be done during screening as one must be within 7 days of starting treatment.

6.3.1.6 Laboratory Assessments

Abnormalities in clinical laboratory tests that lead to a change in subject management (e.g., dose delayed [withheld] or reduced, requirement for additional medication, treatment or monitoring) are considered clinically significant for the purposes of this study, and will be recorded on the Adverse Events Case Report Form (CRF). If laboratory values constitute part of an event that meets criteria defining it as serious, the event (and associated laboratory values) must be reported as an SAE.

| Laboratory Assessments | | |
|---|---|---|
| Hematology | | |
| 
 • WBC count with differential (including at minimum: neutrophils, basophils, eosinophils, lymphocytes, monocytes) | 
 • hematocrit • platelet count • RBC count • hemoglobin | |
| Serum chemistry | | |
| 
 • albumin • ALP • amylase • ALT • AST • bicarbonate • BUN • chloride | 
 • creatinine • GGT • glucose • ionized calcium or total and corrected calcium • lactate dehydrogenase • lipase | 
 • magnesium • phosphorus • potassium • sodium • total bilirubin • total protein |
| Urinalysis | | |
| 
 • appearance • color • pH • specific gravity • ketones • protein • UPCR | 
 • glucose • bilirubin • nitrite • creatinine • urobilinogen | 
 • occult blood (microscopic examination of sediment will be performed only if the results of the urinalysis dipstick evaluation are positive) |
| Other | | |
| 
 • TSH, Free T3 and T4 • Pregnancy test (urine or serum) for women of child-bearing potential | 
 • PT/INR, PTT • CA19-9 | |

CONFIDENTIAL

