Table 4-2: Dose Reductions of Cabozantinib and Erlotinib

| Assigned Starting Dose | First Dose Level Reduction |
|-------------------------------|---|
| 40-mg cabozantinib oral qd | 20-mg cabozantinib oral qd (discontinue if this dose is not tolerated) |
| 100-mg erlotinib oral qd | 50-mg erlotinib oral qd (discontinue if this dose is not tolerated) |

See Section 4.5.5 for complete details regarding potential drug interactions.

CONFIDENTIAL

Table 4-3: Dose Modifications for Treatment-Related AEs for Cabozantinib and Erlotinib

Dose modifications should be made to both cabozantinib and erlotinib for any overlapping treatment-related adverse events unless the investigator suspects one drug over another to be the cause of unacceptable toxicity. In this case, dose modifications may be made to one drug per the investigator's discretion. The most common overlapping toxicities are: diarrhea, fatigue, nausea, skin reactions and vomiting.

| CTCAE v.4.03 Grade | Recommended Guidelines for Management^a |
|--|---|
| Grade 1 AEs | Add supportive care as indicated. Continue treatment at the current dose level if AE is manageable and tolerable. |
| Grade 2 AEs which are tolerable and are easily managed | Continue treatment at the current dose level with supportive care. |
| Grade 2 AEs which are intolerable and cannot be adequately managed | At the discretion of the investigator, treatment should be dose reduced or interrupted. Note: It is recommended that dose holds be as brief as possible. |
| Grade 3 AEs (except clinically non-relevant laboratory abnormalities) | Treatment should be interrupted unless the toxicity can be easily managed with a dose reduction and optimal medical care. Note: It is recommended that dose holds be as brief as possible. |
| Grade 4 AEs (except clinically non-relevant laboratory abnormalities) | Subjects should have treatment interrupted immediately. Discontinue treatment unless the following criteria are met: 
 • Subject is deriving clear clinical benefit as determined by the investigator and agreed by the sponsor-investigator • Toxicity can be managed with a dose reduction following recovery to Grade 1 (or baseline) and optimal medical care |

Note: The dose delay and modification criteria for specific medical conditions are provided in Section 4.3.1. For re-treatment criteria of study treatment after a dose hold see Section 4.3.2.

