7 SAFETY

7.1 Definitions of Adverse Events

7.1.1 Adverse Events

An AE is any untoward medical occurrence in a patient or clinical investigation subject who has been enrolled in a clinical study and who may have been given an investigational product, regardless of whether or not the event is assessed as related to the study treatment. An AE can therefore be any unfavorable and unintended sign (including an abnormal laboratory finding), symptom, or disease temporally associated with the use of an investigational product, regardless of whether or not the event is assessed as related to the investigational product. Pre-existing medical conditions that worsen during a study should be recorded as AEs. Abnormal laboratory values, ECG findings, or vital signs are to be recorded as AEs if they meet the criteria described in Section 4.3 and 4.4.

All untoward events that occur after patient begins study treatment through 30 after the decision to discontinue study treatment (or the date the subject is deemed to be a screen failure) are to be recorded by the investigational site. This requirement includes AEs from unscheduled as well as scheduled visits.

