7.3 Other Safety Considerations

7.3.1 Laboratory Data

All laboratory data required by this protocol and any other clinical investigations should be reviewed. Any abnormal value that leads to a change in subject management (e.g., dose reduction or delay or requirement for additional medication or monitoring) or that is considered to be of clinical significance by the investigator should be reported as an AE or SAE as appropriate.

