8.8 Safety Analysis

The safety population will be used for all safety analysis. All safety data will be listed. For the treatment-emergent AEs, namely AEs started or worsened during the on-treatment period, the incidence will be summarized by system organ class and/or preferred term, severity based on CTCAE grades, type of adverse event and the relation to the study drug. Deaths reportable as SAEs and non-fatal serious adverse events will be listed by patient and tabulated by type of adverse event.

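### Three sections set different triggers for recording a laboratory value as an AE, and laboratory toxicity reaches the incidence tables only through AE records

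*Combined protocol and SAP*

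**What the plan says.** Three sections of the protocol address when an abnormal laboratory value becomes an AE.

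- **Section 6.3.1.6 (Laboratory Assessments):** "Abnormalities in clinical laboratory tests that lead to a change in subject management" "are considered clinically significant for the purposes of this study, and will be recorded on the Adverse Events Case Report Form (CRF"). The examples include added medication, treatment or monitoring as well as dose changes.
- **Section 7.3.1 (Laboratory Data):** the same management trigger, extended by "or that is considered to be of clinical significance by the investigator should be reported as an AE or SAE as appropriate".
- **Section 7.1.1 (Adverse Events):** abnormal laboratory values, together with ECG findings and vital signs, "are to be recorded as AEs if they meet the criteria described in Section 4.3 and 4.4". Earlier in the same section the general definition is wider, since an AE can be "any unfavorable and unintended sign (including an abnormal laboratory finding").

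On the analysis side, Section 8.3 defines the safety endpoint as AE terms entered on the electronic case report form. Section 8.8 promises a listing of all safety data and a table of deaths and SAEs. For "AEs started or worsened during the on-treatment period, the incidence will be summarized by system organ class and/or preferred term", grade and relationship. It names no table of laboratory grades and no shift table. Section 8.1 promises summaries of safety outcomes in general terms, without naming laboratory data.

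**The concern.** A count of patients with, say, a Grade 3 laboratory abnormality should follow from the measured values. Under this plan it follows from whether a value was entered as an AE, and the entry rule differs between sections. Two staff members who each follow the section nearest to hand could record the same result differently.

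Safety and tolerability is a secondary objective (Section 3.1.2). Section 4.4 names many laboratory-associated events seen with cabozantinib in at least 5% of subjects, including raised transaminases, raised lipase, electrolyte disturbances and cytopenias. Section 9.1 requires the DSMC chair to be told if Grade 3 or higher AEs become more frequent than the reference documents report. In a small single-arm trial, a few unrecorded values would visibly change a tabulated rate.

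**Working it through.** The plan states no figure on this point, so there is none to reproduce. The check is a comparison of the texts, followed by an illustration on assumed inputs.

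**Step 1. Apply each rule to one case.** Take a Grade 3 lipase value on which nobody acts.

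| Source | Is it recorded as an AE? |
|---|---|
| 6.3.1.6 | Not triggered, because management did not change |
| 7.3.1 | Yes if the investigator considers it clinically significant, otherwise not triggered |
| 7.1.1, reference to 4.3 and 4.4 | Unclear (Step 3) |
| 7.1.1, general definition | It can be an AE |

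**Step 2. How the rules relate.** The trigger in 6.3.1.6 is the first limb of 7.3.1, so the former is contained in the latter. The two differ only in the judgement limb. The clearest mismatch is 7.1.1 against both.

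**Step 3. Does the reference in 7.1.1 work as a recording rule?** Sections 4.3 and 4.4 mainly say what to do about toxicity, not what to write down.

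- Table 4-3 grades events already called AEs, so using it to decide what is an AE is circular.
- If meeting the criteria means falling in any row, Grade 1 values qualify and 7.1.1 is very wide. If it means falling in a row that calls for action, 7.1.1 is narrow. The relevant row reads "Grade 3 AEs (except clinically non-relevant laboratory abnormalities"), and the Grade 4 row carries the same exception.
- The footnote to Table 4-3 ties dose adjustment to toxicity that is related, or of unclear relationship, to treatment. Section 7.1.1 defines AEs regardless of relationship.
- Some scheduled tests in 6.3.1.6, such as lipase, amylase and sodium, have no subsection of their own in 4.4.1, so only the general Table 4-3 is left.

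**Step 4. Follow a value to the tables.** A value recorded as an AE enters the 8.8 incidence summary, and one that is serious also enters the SAE table. A value not recorded as an AE appears only in a listing. A listing allows a later count but does not define a rate, a baseline comparison or a time window.

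**Step 5. Illustration.** Let q be the true share of patients with a given graded abnormality, and f the share of those patients in whom it is recorded as an AE. The tabulated rate is q × f. The documents give neither, so all values below are assumptions.

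| q | f = 1 | f = 0.75 | f = 0.5 | f = 0.25 |
|---|---|---|---|---|
| 10% | 10% | 7.5% | 5% | 2.5% |
| 20% | 20% | 15% | 10% | 5% |
| 30% | 30% | 22.5% | 15% | 7.5% |

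For q = 20% and 37 patients, 0.20 × 37 = 7.4 patients have the abnormality. At f = 0.5, 7.4 × 0.5 = 3.7 are tabulated. The 37 is the two-stage efficacy total. The safety population is everyone dosed, from a trial with 11 patients in its first stage and up to 40 enrolled. The percentages do not depend on that number.

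**The case against.** The strongest reply is that the sections are cumulative. Section 6.3.1.6 gives a sufficient trigger and does not say that nothing else counts. Section 7.3.1 adds to it, and the definition in 7.1.1 is wider still. A site that follows all three records the union, which could capture every relevant value. This stands as a possible reading. But the protocol never states it, and the 7.1.1 limb would remain undefined under it.

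A reader might also infer that Table 4-3 lets unacted-on Grade 3 and 4 values go unrecorded. The table does not support that. It governs dosing, not recording, and its wording treats the excepted abnormalities as a kind of AE.

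A reader might further infer that the Section 9.1 comparison is invalid. That comparison is of AEs with reference documents, and the protocol does not say how those documents compiled their rates. One can say only that the rates may not be comparable.

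Finally, 8.8 does list all safety data, and in a trial of this size graded abnormalities could be counted by hand from the listing. That is true, but such a count is not planned.

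**Conclusion.** The inconsistency is real: three overlapping triggers, no governing rule, and one of them pointing to guidance not written as a recording rule. The consequence is also real but limited. Planned laboratory incidence depends on the rule applied and on investigator action or judgement, and may be lower than the rate from CTCAE-graded values.

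It is tempting to say that laboratory toxicity is understated. The documents do not support that, because 7.3.1 and the general definition in 7.1.1 allow wide capture. On the assumed inputs above, a 20% rate could be tabulated as anything from 5% to 20%, and the upper end is no shortfall at all. The table shows how the mechanism works and does not estimate its size. This is a minor point, worth acting on because the remedy uses data already collected.

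**What to change.** 1. **Section 8.8.** For the safety population, add a table of worst post-baseline CTCAE v4.03 grade, with shift from baseline grade, for each scheduled laboratory test that has a CTCAE grade. Compute it from the recorded values, state the post-baseline window, and show it beside the AE table. Tests without a grade, such as urine color, drop out. Section 6.1 already schedules chemistry and hematology before the first dose, during treatment and at the post-treatment visit.
2. **Sections 6.3.1.6, 7.1.1 and 7.3.1.** Reconcile the laboratory recording rule into one criterion, for example the 7.3.1 wording, and refer to it from the other two. Keep a rule for ECG findings and vital signs in 7.1.1, since the present sentence covers them too.

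The table matters more than the wording. Under the 7.3.1 rule, AE recording would still depend on action or judgement, whereas a table from the values does not.

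The cost is one derived table and a text edit. Section 8.1 allows analysis changes without a protocol amendment unless a significant feature changes; the recording-rule edit is a change to protocol text and should follow Section 11.3. The downside is that reported laboratory toxicity may look higher than the AE-based rate, so both tables should be labeled with their basis.
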